- Intent-to-Treat (ITT) population will include all subjects who are randomized.
- vIGA-AD Moderate ITT population will be a subset of the ITT population with vIGA-AD score 'moderate' at randomization.
- WI-NRS population will be a subset of the ITT population with a baseline WI-NRS score ≥ 4.
- PK population will include all subjects receiving the active drug with quantifiable plasma concentrations of roflumilast.

To control for multiple comparisons, the key secondary endpoint will only be tested if the primary endpoint demonstrates statistical significance. In addition, the remaining secondary endpoints will be inferentially tested only if the primary and key secondary endpoint comparisons are statistically significant. To control for multiple comparisons among the remaining secondary endpoints, partitioning of alpha and the Holm's procedure will be used.

[figure not shown]
Descriptive statistics for continuous variables will include mean, median, standard deviation, min, max. Descriptive statistics for categorical variables will include frequencies and percents. For missing data, the primary imputation method and sensitivity methods will be detailed in the SAP. The primary endpoint and key secondary endpoints of vIGA-AD success will be analyzed with a Cochran-Mantel-Haenszel test stratified by the randomization factors (disease severity determined by vIGA-AD and by study site).

Categorical secondary efficacy analysis will be analyzed in the same manner as the primary endpoint.

Continuous secondary endpoints will be analyzed analysis of covariance with treatment, the randomization stratification factors, and baseline value as independent variables. Statistical comparisons between the treatment groups will be obtained using contrasts.

The incidence of adverse events will be summarized as well as changes in laboratory parameters and vital signs.

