6 STATISTICAL CONSIDERATIONS

6.1 Adjustments for Covariates

Covariates for this study include pooled study site and baseline vIGA-AD (vIGA-AD=2 - Mild vs. vIGA-AD=3 - Moderate at randomization). Subgroup analyses will be generated for the baseline covariates.

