2. Once the monotone pattern is achieved, the next step is to implement the imputation algorithm. For this, the PMM regression method will be used. This method is particularly helpful if the normality assumption is violated. For subjects with complete data up to a particular visit, a PMM regression model will be fit that includes the outcome at that visit as the dependent variable and as independent variables, the treatment group, pooled study site, and vIGA-AD score outcomes at previous visits, using a seed of 482371. For other scales/questionnaires, the actual baseline vIGA score will also be included as an independent variable. This process will be repeated 25 times, resulting in a total of 25 to 250 complete analysis datasets, depending on the number of imputed monotone datasets that are required. The seed may be changed after unblinding in case of any issues with the imputation process, and it will be documented in the CSR if any change is required.
3. For each of the 25 to 250 completed dataset, the necessary derived variable will be computed as defined in Section 5.5 and analyzed using a CMH analysis, adjusted for the pooled study site and randomized vIGA-AD score for the primary efficacy endpoint and adjusted for the pooled site for the secondary efficacy endpoint. Results will be combined into one multiple imputation inference as follows:
 - a. Common proportion of success, common Mantel-Haenszel (MH) proportion difference (and associated 95% CI), and common MH odds ratio (and associated common 95% CI) will be combined using PROC MIANALYZE based on Rubin's rule. Common MH odds ratios and associated common 95% CI will first be normalized using a log-transformation before being combined using PROC MIANALYZE. The resulting combined common MH odds ratio and associated combined common 95% CI will be back-transformed to the arithmetic scale before being presented in a table.
 - b. For the combined common proportion of success, the associated combined common 95% CI will be calculated as per Lott and Reiter multiple imputation Wilson interval method¹.
 - c. Two p-values will be produced for each analysis:
 - i. The primary p-value will be obtained from a multiple imputation CMH test, where CMH general association statistics and their standard errors obtained

	STATISTICAL ANALYSIS PLAN, Version 3.0
Protocol Number: ARQ-151-311	Sponsor: Arcutis Biotherapeutics, Inc.

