12.1.3 Primary Endpoint Analysis

For the primary analysis, missing vIGA-AD scores will be imputed using multiple imputation as described in Section 6.2.1. These imputations will result in a minimum of 25 to a maximum of 250 complete analysis datasets, depending on the number of imputed monotone datasets that are required.

Percentages of subjects having a vIGA-AD Success (refer to Section 12.1.1) will be presented by visit and treatment group based on multiply imputed data in the ITT population along with a 95% Wilson CI. The common MH odds ratio and common MH proportion difference, adjusted for the randomization factors (i.e., randomized vIGA-AD score and pooled study site) will also be provided along with their common associated 95% CIs. Additionally, count and percentage of subjects having a vIGA-AD success, count and percentage of subjects in each category of the vIGA-AD scale, and descriptive statistics for the vIGA-AD scores, change in vIGA-AD score from

	STATISTICAL ANALYSIS PLAN, Version 3.0
Protocol Number: ARQ-151-311	Sponsor: Arcutis Biotherapeutics, Inc.

baseline and percent change in vIGA-AD score from baseline will be presented by visit and treatment group based on observed data in the ITT population.

The primary endpoint (vIGA-AD Success at Week 4) will then be analyzed using multiple imputation CMH test stratified by the randomization factors. To do so, a CMH analysis will be performed separately for each of the complete multiply imputed analysis data sets, and results will be combined into one multiple imputation inference using the methodology described in Section 6.2.1. Statistical significance will be concluded at the 5% significance level (2-sided). Should the odds ratio be not estimable for at least one multiply imputed dataset, the conclusion of the study will be based on the p-value obtained from a MH test, stratified by the randomization factors, for the common MH proportion difference at Week 4.

The following sensitivity analyses to the primary analysis of the primary endpoint will be performed:

- Multiply-imputed data (refer to Section 6.2.1) on mITT population (refer to Section 4.2) and
- Tipping Point analysis (refer to Section 6.2.3) on ITT population.
- Non-responder imputation (refer to Section 6.2.2) on ITT population.
- Observed data on ITT population (refer to Section 4.1).
- Observed data on PP population (refer to Section 4.3).

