endpoint family 1, comprised of the 4-point reduction on the average weekly WI-NRS at Week 4, Week 2 and Week 1, and secondary endpoint family 2, comprised of the EASI-75 at Week 4, vIGA-AD of ‘clear’ or ‘almost clear’ at Week 4, vIGA-AD of success at week 2 and week 1, vIGA-AD of ‘clear’ or ‘almost clear’ at Week 2 and Week 1. The analysis of secondary endpoint family 1 will be performed as described for the primary efficacy endpoint (refer to Section 12.1.3) but based on the WI-NRS population (refer to Section 4.6) and an alpha level of 0.03 will be used to test these endpoints sequentially as described in Section 6.5. Similarly, the analysis of secondary endpoint family 2 will be performed as described for the primary efficacy endpoint (refer to Section 6.2.1) based on the ITT population (refer to Section 4.1) but an alpha level of 0.02 will be used to test these endpoints sequentially as described in Section 6.5.

Secondary Endpoint Family 1 ($\alpha=0.03$, hierarchical testing)

- In subjects ≥ 12 years old with baseline WI-NRS ≥ 4 , achievement of at least a 4-point reduction in the average weekly WI-NRS at Week 4
- In subjects ≥ 12 years old with baseline WI-NRS ≥ 4 , achievement of at least a 4-point reduction in the average weekly WI-NRS at Week 2
- In subjects ≥ 12 years old with baseline WI-NRS ≥ 4 , achievement of at least a 4-point reduction in the average weekly WI-NRS at Week 1

Secondary Endpoint Family 2 ($\alpha = 0.02$, hierarchical testing)

- Achievement of at least a 75% reduction in the Eczema Area and Severity Index at Week 4 (EASI-75)
- vIGA-AD of ‘clear’ or ‘almost clear’ at Week 4
- vIGA-AD Success at Week 2
- vIGA-AD Success at Week 1
- vIGA-AD of ‘clear’ or ‘almost clear’ at Week 2
- vIGA-AD of ‘clear’ or ‘almost clear’ at Week 1

For the secondary efficacy endpoint of vIGA-AD Success at Week 4 based on the vIGA-AD moderate ITT population, the following sensitivity analyses to the primary analysis of this efficacy endpoint will be performed if and only if the hierarchical testing procedure (refer to Section 6.5) allows it:

- Tipping Point analysis (refer to Section 6.2.3) on vIGA-AD moderate ITT population.

	STATISTICAL ANALYSIS PLAN, Version 3.0
Protocol Number: ARQ-151-311	Sponsor: Arcutis Biotherapeutics, Inc.

- Non-responder imputation (refer to Section [6.2.2](#)) on vIGA-AD moderate ITT population.
- Observed data on vIGA-AD moderate ITT population.

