For each categorical exploratory efficacy endpoint, count and percentages of subjects meeting the criteria for an exploratory efficacy endpoint will be presented by visit and treatment group based on observed data in the ITT population along with a 95% Wilson CI. Additionally, count and percentage of subjects meeting the criteria for vIGA-AD of Clear (0), EASI-50, EASI-90, and EASI-100 at Week 1 and Week 2 will also be presented by visit and treatment group based on observed data in the ITT population along with a 95% Wilson CI.

Continuous exploratory efficacy endpoints will be analyzed at Week 1, Week 2, and Week 4 and for daily WI-NRS assessments using an analysis of covariance (ANCOVA) with the factors of treatment, two stratification variables (pooled study site and randomized vIGA-AD score), and baseline of the variable under analysis as covariate. Statistical comparisons between the treatment groups will be obtained using contrasts. The Least Square (LS) mean and its standard error, difference in LS means between treatment group (i.e., active - vehicle), its standard error and associated 95% confidence interval, and p-value for difference from vehicle will be presented at each visit. These analyses will be performed based on observed data in the ITT population.

Categorical exploratory efficacy endpoints at Weeks 1, 2, and 4 will be analyzed using a CMH test adjusted for the two stratification variables (pooled study site and randomized vIGA-AD score). Common MH odds ratio, common MH proportion difference and their common associated 95% CI, adjusted for the randomization factors, will be provided. The p-value will be from a CMH test for the common MH odds ratio, unless the common MH odds ratio is not estimable. In such circumstances, the p-value will be from a MH test for the common MH proportion difference.

The analysis of these endpoints will be performed on the observed data with no imputation. The p-values will be nominal as no formal inferential testing will be done on exploratory efficacy endpoints.

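### The Family 1 itch responder tests do not adjust for baseline WI-NRS, which an absolute 4-point threshold makes a likely predictor of response: a possible loss of precision, not of validity

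*SAP*

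**What the plan says.** SAP 6.1 declares two covariates: "Covariates for this study include pooled study site and baseline vIGA-AD", the latter as mild versus moderate at randomization. SAP 12.1.3 builds the primary CMH test on those two factors, and SAP 12.2 carries it over: "The analysis of secondary endpoint family 1 will be performed as described for the primary efficacy endpoint", on the WI-NRS population at alpha 0.03. EASI-75 gets the same treatment: "the analysis of secondary endpoint family 2 will be performed as described for the primary efficacy endpoint". The protocol synopsis has the same rule: "Categorical secondary efficacy analysis will be analyzed in the same manner as the primary endpoint".

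The WI-NRS population (SAP 4.6) is subjects aged 12 or over with at least 4 of 7 evaluable daily scores before treatment and a mean of at least 4.0. Success (SAP 5.5) is a 4-point fall in the weekly average.

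Baseline scores appear in four other places:
- The imputation model uses "vIGA-AD score outcomes at previous visits", with a similar method for WI-NRS and EASI (SAP 6.2.1).
- Baseline WI-NRS and EASI are tabulated (SAP 8).
- Baseline EASI is a subgroup factor (SAP 6.6); baseline WI-NRS is not.
- The ANCOVA for exploratory continuous endpoints uses "two stratification variables (pooled study site and randomized vIGA-AD score), and baseline of the variable under analysis as covariate" (SAP 12.3).

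None of these adjusts the responder tests. The sensitivity analyses listed for those endpoints (SAP 12.2 and 12.5) are non-responder imputation and observed data. Both change only the handling of missing values.

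**The concern.** With an absolute threshold, the starting score is part of what makes success easy or hard. A subject entering at 4.0 must report no itch on every recorded day of the week; a subject entering at 9 need only average 5. Randomized vIGA-AD is a weak stand-in for itch: it grades visible signs, and its instructions (Protocol Appendix 7) say excoriations should not be considered. Baseline itch is not a randomization factor, so the arms are balanced on it only by chance.

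Adjusting for a baseline variable that predicts response sharpens a comparison at no cost in subjects. That matters here because Family 1 is a fixed sequence: all three itch tests must pass at 0.03 before that alpha moves to Family 2 (SAP 6.5). A small loss on each test accumulates across the gate.

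**Working it through.** **The plan's own figures.** No power is stated for the itch tests. SAP 5.1 gives about 95% for the primary endpoint (650 subjects, 2:1, 37% v 22%) and about 90% for the moderate subset (490 subjects, 45% v 28%). With

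power = Φ[(d − z·SE0)/SE1],

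where d is the difference in rates, SE0 uses the pooled variance and SE1 the unpooled, the primary gives (0.15 − 1.96 × 0.0388)/0.0365 = 2.03, or 97.9%. The moderate subset gives 96.0%. Both exceed the stated figures. That is a separate matter and does not bear on this point.

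**Inputs.** From the documents: 2:1 allocation, two-sided alpha 0.03, threshold 4 points, baseline at least 4.0. Assumed: size of the WI-NRS population, response rates, and the correlation r between baseline and response.

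**Approximate size by hand.** Adjusting for a baseline variable with correlation r acts like multiplying the sample size by 1/(1 − r²). Take N = 300 and 37% v 22%. Unadjusted: (0.15 − 2.170 × 0.0571)/0.0537 = 0.485, power 68.6%.

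| r | 1/(1 − r²) | Power unadjusted | Power adjusted |
|---|---|---|---|
| 0.10 | 1.010 | 68.6% | 69.1% |
| 0.20 | 1.042 | 68.6% | 70.6% |
| 0.34 | 1.131 | 68.6% | 74.6% |

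**Simulation, strata held fixed.** 2:1 allocation, 25 pooled sites × 2 severities, baseline 4 to 10, response about 38% v 19%, alpha 0.03. The planned CMH test is compared with the same CMH test on residuals from a treatment-blind logistic fit on baseline, so any gain is due to baseline alone.

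| r | N | Planned CMH | Baseline-adjusted CMH |
|---|---|---|---|
| 0.10 | not recorded | 0.828 | 0.830 |
| 0.20 | 320 | 0.914 | 0.928 |
| 0.25 | 240 | 0.785 | 0.813 |
| 0.34 | 240 | 0.736 | 0.798 |

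Under the null both tests reject at 0.031 to 0.032. A second simulation of the same comparison gave gains of about 1 to 4 points at r of about 0.27 to 0.36, no material change at about 0.11, and null rejection rates of 0.029 and 0.027.

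**How large might r be?** The documents do not say. In an illustrative itch model, baseline explained about 1% to 13% of response variance (r about 0.1 to 0.36), less as the correlation between baseline and Week 4 itch rose from 0.2 to 0.6.

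**All three itch tests passing.** Assumed response at Weeks 4/2/1: 43/32/23% v 20/14/10%, with correlated visits and 18 pooled sites × 2 severities.

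| r | N = 240 | N = 320 | N = 400 |
|---|---|---|---|
| 0.34 | 52.0 to 57.8% | 71.7 to 77.6% | 84.3 to 88.4% |
| 0.25 | 55.2 to 58.5% | 75.1 to 77.5% | 87.6 to 90.0% |

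At r = 0.15 the gain is about 1 point; at 0.05 there is no material change.

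**Chance imbalance.** A 2-SD imbalance in baseline itch (about 0.35 points) moves the unadjusted difference by about 2 to 4 percentage points. The standard error at 38% v 19% and N = 240 is √(0.38 × 0.62/160 + 0.19 × 0.81/80) = 5.8 points (5.0 at N = 320). Even a rare imbalance moves the estimate by less than one standard error.

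**EASI-75.** N = 650, alpha 0.02, a 15-point effect and an assumed baseline odds ratio per SD of 1.5, 2.0 or 3.0. A model with site and vIGA-AD gives 95.4, 95.1 and 95.9%; adding baseline gives 95.9, 96.4 and 98.2%.

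**The case against.** The strongest reply is that nothing is broken. The SAP applies the protocol's rule for categorical endpoints, the test is valid under randomization, and its standard error already reflects chance imbalance. Every size given above rests on assumptions. An adjusted p-value also comes without a matching effect estimate. All of this stands, and it makes this a recommendation about efficiency.

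Several stronger readings are tempting, and the documents do not support them:

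- **SAP 12.3 shows the alpha-controlled tests were given less care.** The split is by type of data. Exploratory categorical endpoints such as EASI-50 and EASI-90 also use CMH without a baseline score.
- **The same argument covers EASI-75.** That endpoint is a percentage reduction already scaled to baseline, and vIGA-AD grades three of EASI's four signs. A strong further link to baseline cannot be assumed.
- **Baseline imbalance goes uncorrected.** Stratifying by vIGA-AD removes some severity imbalance, mainly for EASI. The tabulated baselines and the baseline-adjusted ANCOVA would make an itch imbalance visible.
- **Family 2 suffers materially.** At 37% v 22% and N = 650, the first Family 2 test has 94.9% power at alpha 0.02 and 97.9% at 0.05. A 6-point rise in Family 1 success would add only about 0.06 × 3.0 = 0.2 points to that test.

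What the reply does not answer is that the itch threshold is absolute, the covariate is already in hand, and no baseline-adjusted analysis of these responder endpoints is planned even as support.

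**Conclusion.** The point holds for the three Family 1 itch tests as a conditional loss of precision. Type I error is nominal with or without the adjustment. If baseline-response correlation is about 0.2 to 0.36, adjustment gains about 1 to 6 power points per test, and roughly 2 to 6 points on the chance that all three pass when it is 0.25 to 0.34. If it is near 0.1, the gain is negligible, and so is the cost. A link between baseline and response is plausible from the endpoint definition, but the documents give no figure for its strength, so it should not be stated as fact that baseline drives response or that power is lost. For EASI-75 the case supports no more than a supportive analysis.

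**What to change.** Before unblinding, amend SAP 6.1 and 12.2 for Family 1:

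- In each imputed dataset, fit a logistic regression of 4-point response on continuous average weekly baseline WI-NRS, with no treatment term.
- Run the stratified CMH row-mean-score test on the residuals, using the same pooled site × randomized vIGA-AD strata. With two arms it has one degree of freedom, as the planned statistic has, so the combination by Rubin's rules in SAP 6.2.1 carries over.
- Keep the population, imputation, alpha and test order unchanged.
- Keep the common MH odds ratio and proportion difference as the reported effect estimates, and the unadjusted CMH test as a sensitivity analysis.
- Record the departure from the protocol's categorical rule in SAP 3.5. The protocol text at hand is the original version, while the SAP cites Amendment 4, so check the rule there.

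For EASI-75, at most add a supportive analysis adjusted for baseline EASI, with a stated rule for missing baseline values; SAP 6.2.2 allows that some may be missing.

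The cost is SAP wording and a few lines of code, with no new data. The downside is that the Family 1 p-value and the reported MH estimates would no longer come from the same statistic, which the SAP should say openly.

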6.2 Handling of Dropouts or Missing data

See [Appendix 2](#) for handling of completely or partially missing dates for prior and concomitant medications and AEs.

Unless otherwise specified, missing safety data will not be imputed.

6.2.1 Multiple Imputation

All subjects, regardless of completion status, will have available data assigned to the pre-specified analysis visit using the analysis windows defined in Section [5.4](#), including the last available data

	STATISTICAL ANALYSIS PLAN, Version 3.0
Protocol Number: ARQ-151-311	Sponsor: Arcutis Biotherapeutics, Inc.

of subjects who prematurely withdraws from the study. To comply with the definition of the primary estimand (Section 12.1.1), for subjects who discontinue due to lack of efficacy or adverse event, efficacy data assigned to a pre-specified analysis visit will be removed from the source data used for the multiple imputation process if subject's last dose day falls within the analysis visit window or is prior to the start of the analysis visit window used to assign data to a pre-specified analysis visit. Similarly, WI-NRS weekly averages will be removed from the source data used for multiple imputation if subject's last dose day falls within the analysis visit window or is prior to the start of the interval used to compute the weekly average as defined in Section 5.4. This procedure will ensure that the data collected on or after intercurrent events are not used in the imputation process.

For the primary efficacy endpoint of vIGA-AD success at Week 4 and the secondary endpoint of vIGA-AD success at Week 4 among subjects with a 'Moderate' randomized vIGA-AD score, the primary analysis will impute missing values using a Predictive Mean Matching (PMM) sequential-regression multiple imputation model for the ITT population. This is a three-step process.

1. The first step is to understand the pattern of missingness. In order to perform the multiple imputation, a monotone missing pattern has to be achieved. For example, if there exist values for baseline and Week 4 visits, but missing values for the Week 1 or 2 visits, the Markov-Chain Monte-Carlo (MCMC) method will be used to impute the small amount of missing data that may be missing at the intermediate visits that is required to make the missing data pattern monotone before applying the multiple imputation algorithm. This method uses a non-informative Jeffreys prior to derive the posterior mode from the expectation-maximization (EM) algorithm as the starting values for the MCMC method. The MCMC method will use the seed 6457149. The vIGA-AD score will be treated as a continuous variable for this step and the model will include the vIGA-AD scores at baseline, Week 1, Week 2, and Week 4. To avoid values that could not be observed in practice, imputed values will be rounded to the nearest integer (Round=1 option in PROC MI) in the range of 0 to 4.

To determine the number of multiply-imputed datasets to be created at this step, the proportion of datapoints with non-monotone pattern across all visits and subjects will first be derived as follows:

$$\frac{\text{number of non monotone visits accross all visits and subjects}}{\text{total number of expected visits across all subjects}} * 100$$

Then, the following table will be used:

	STATISTICAL ANALYSIS PLAN, Version 3.0
Protocol Number: ARQ-151-311	Sponsor: Arcutis Biotherapeutics, Inc.

Non-monotone Missing Data	Number of Imputed Datasets
$\leq 2\%$	1
$> 2\% \text{ to } \leq 5\%$	3
$> 5\%$	10

2. Once the monotone pattern is achieved, the next step is to implement the imputation algorithm. For this, the PMM regression method will be used. This method is particularly helpful if the normality assumption is violated. For subjects with complete data up to a particular visit, a PMM regression model will be fit that includes the outcome at that visit as the dependent variable and as independent variables, the treatment group, pooled study site, and vIGA-AD score outcomes at previous visits, using a seed of 482371. For other scales/questionnaires, the actual baseline vIGA score will also be included as an independent variable. This process will be repeated 25 times, resulting in a total of 25 to 250 complete analysis datasets, depending on the number of imputed monotone datasets that are required. The seed may be changed after unblinding in case of any issues with the imputation process, and it will be documented in the CSR if any change is required.
3. For each of the 25 to 250 completed dataset, the necessary derived variable will be computed as defined in Section 5.5 and analyzed using a CMH analysis, adjusted for the pooled study site and randomized vIGA-AD score for the primary efficacy endpoint and adjusted for the pooled site for the secondary efficacy endpoint. Results will be combined into one multiple imputation inference as follows:
 - a. Common proportion of success, common Mantel-Haenszel (MH) proportion difference (and associated 95% CI), and common MH odds ratio (and associated common 95% CI) will be combined using PROC MIANALYZE based on Rubin's rule. Common MH odds ratios and associated common 95% CI will first be normalized using a log-transformation before being combined using PROC MIANALYZE. The resulting combined common MH odds ratio and associated combined common 95% CI will be back-transformed to the arithmetic scale before being presented in a table.
 - b. For the combined common proportion of success, the associated combined common 95% CI will be calculated as per Lott and Reiter multiple imputation Wilson interval method¹.
 - c. Two p-values will be produced for each analysis:
 - i. The primary p-value will be obtained from a multiple imputation CMH test, where CMH general association statistics and their standard errors obtained

	STATISTICAL ANALYSIS PLAN, Version 3.0
Protocol Number: ARQ-151-311	Sponsor: Arcutis Biotherapeutics, Inc.

from the analysis of each multiply-imputed dataset will be transformed as per Wilson-Hilferty² before being combined using PROC MIANALYZE based on Rubin's rule. Because the Wilson-Hilferty transformation is a monotone transformation, the p-value for the CMH test is the one-sided p-value from the t distribution. This p-value will be the primary p-value used to evaluate the result according to the multiple testing strategy described in Section 6.5.

- i. Should the common MH odds ratio from the analysis of at least one of the multiply-imputed datasets be not estimable, combined common MH odds ratio and associated combined common 95% CI and p-value will not be presented. Under such circumstance, conclusions will be based on the p-value obtained from a multiple imputation test of the proportion difference, where the common proportion difference using MH weights and associated common standard errors based on the Sato variance estimator obtained from the analysis of each multiply-imputed dataset will be combined using PROC MIANALYZE based on Rubin's rule.

Similar multiple imputation method will be used for the average weekly WI-NRS and EASI total score.

For the average weekly WI-NRS (refer to Section 5.5), it's the missing average weekly WI-NRS data (i.e., those that cannot be computed because only 3 or less non-missing assessments are available during a given week) at Weeks 1, 2, 3, and 4 that will be multiply imputed, not the missing daily WI-NRS data. Since the missing average weekly WI-NRS values have a precision of 1 decimal place, the MCMC imputation for the non-monotone missing data will be restricted to values between 0 and 10, rounded to the 1st decimal (i.e., 0.1). Imputation of missing data for WI-NRS will be based on the ITT population, i.e., all randomized subjects will be included in the imputation process.

For the EASI total score (refer to Section 5.5), it's the missing EASI total score data at Weeks 1, 2, and 4 that will be imputed, not the missing EASI question score data. Since the missing EASI total scores have a precision of 1 decimal place, the MCMC imputation for the non-monotone missing data will be restricted to values between 0 and 72, rounded to the 1st decimal (i.e., 0.1). Imputation of missing data for EASI total score will be based on the ITT population.

